7.3 Selection of Slides for Feature Detection

Glass slides shall be chosen per the procedure below and consistent with the inclusion and exclusion criteria for the study provided it has the specific feature required for that search. The exact slides, features, organs, and magnifications needed for the study are described in [Table 1](#) and are the same for each of the three sub-studies all enrolled from the first site (Ohio State University Wexner Medical Center).

The coordinator and/or EP shall search the first site's database to locate cases that may contain glass slides with the specific feature from pre-specified organs as required by the protocol. Once the slides are obtained, the cases will be further screened by the EP to determine if they meet inclusion and exclusion criteria in order to be enrolled in the study.

Then, the EP will locate the known feature on the glass slide and the coordinates of the selected feature will be recorded. Also, the EP shall record if any other secondary features from same magnification group listed in [Table 1](#) are within the FOV under the microscope view.

The slide will be scanned immediately to create a WSI image, which shall be a "locator WSI" used by the scanning technician to locate and document the WSI coordinates of the selected feature. The coordinates recorded from this locator WSI will be used to construct the study FOVs for each of the respective study scans for that specific enrolled feature.

Because of the wide variety of cases and features, the EP may seek the consult of other pathologists in the site's practice, as long as these other pathologists are not reader pathologists or VEPs. The Sponsor may choose to purchase known cases. In such a situation, the EP will follow the same procedure for purchased slides.

7.4 Validation of Slides for Feature Detection

The trained VEP will review and confirm the choice of slide, feature coordinates, the designated feature recorded and the presence of any coincidental features in the FOV. If there is a discrepancy of the primary feature determination between the EP and VEP, then both the EP and VEP will convene a consensus meeting to come to a decision. If the EP and VEP cannot come to a consensus decision, then that feature/slide choice shall be disqualified from the study.

The process shall be repeated to select an additional set of slides, labeled as the sham features, which follow the same feature selection criteria, but are not used in the analysis.

For each sham feature 6 slides will be selected from 3 different organs.

7.5 Storage of Slides for Feature Detection

The study and self-familiarization slides, the feature's known description, and organ, and feature coordinate information shall be delivered to the SC for safe and secure storage.

The SC shall:

- a. Collect and store the cases, slides, organ and known feature description
- b. Collect and store log of feature as well as FOV location and coordinates

- c. Place proper de-identification labels (e.g., hide names, numbers, barcodes) on enrolled glass slides with a code known only to the SC, and confirm those labels will not interfere with the scanning process nor affect the integrity of the tissue on the slide
- d. Remove all patient identifiers and assign coded-names to protect patient privacy
- e. Ensure traceability is kept only at the site, stored in a secure location, not shared outside the practice, and kept blinded to reading pathologists

7.6 Preparation of WSI images and Creation of TIFF Files

The SC will provide the slides to the scanning technician.

The slide will be scanned at 40x magnification to create the WSI image into the standard Hamamatsu NDPI file format. For additional iterations, the NanoZoomer will be powered down for at least six hours for a complete cool down before the next scanning session. After each scan, the image quality will be checked. If image quality is not acceptable, scanning may be repeated up to 5 times.

If a slide is broken during the study, a decision will be made to record it as a protocol deviation, or to enroll a replacement slide for an incomplete substudy. The replacement slide will be scanned like the others in its set, but not for substudies already completed.

To make the TIFF FOV images for any enrolled slide, the scanning technician(s) shall utilize the locator WSI (made at screening & enrollment) and the sponsor's programs to create TIFF FOV images of the study scans using the originally recorded coordinates. These locator WSI files will be made at site 1 and shared with site 2 and 3 (See [Figure 9](#))

Figure 9. Steps to Create the TIFF FOV Image

First, the scan technician shall locate the feature in the study scan WSI image, using the coordinate identified from the locator WSI for that feature. The scanning technician will create a series of TIFF FOV images at 10x, 20x, or 40x as specified in [Table 1](#). The pixel density of the TIFF FOV image shall be identical to the designated software, display and driving computer to the end user. The size of the TIFF image shall be consistent with the size normally seen at those magnifications (10, 20 or 40X) under the microscope.

The location of the known feature in that TIFF shall be randomized to different locations in the image, and not always in the center of field.

The TIFF image of the feature FOV will be assigned a de-identified coded name kept confidential by the coordinator in a secure location. The TIFF images will be stored in a password protected secure drive of the NanoZoomer computer for later viewing by the reader pathologists.

The SC shall ensure this information is stored in a secure computer hard disk drive, and/or on a secure folder on the Intranet server with secure access known only to the SC. The reading pathologists shall be blinded to the feature information in the study.

The trained RPs shall be allowed to conduct a self-guided mock feature detection on a small set of training cases in order to become familiar with equipment operation for this study. The PI and sponsor's technical staff will be available for discussion of any questions.

7.7 Reading of TIFF Images

The SC shall provide instructions to the RP as to which TIFF images are to be viewed, and in what order, and which eCRFs are to be filled out.

Upon completion of those activities, the SC shall collect, return and store the materials once again to a secure place.

The SC shall provide the RP with the TIFF images to be read on the Hamamatsu workstation monitor in a pre-established randomized order in a password protected study hard drive or server.

Trained RPs in the selected sites will view the set of TIFF images on the monitor workstation of the NanoZoomer and will be asked to identify all the features of interest against a list of 10 possible choices, i.e., the 7 study feature and 3 sham features for that magnification. The RP will fill out the eCRF for the features identified from that FOV.

The TIFF FOV will be randomly rotated, when repeat readings of the same FOV by the same pathologist occurs. The rotations may be some multiple of 90 degrees only (i.e., 0° [no rotation], 90°, 180° or 270°).

When given the set of TIFF images for that reading, we anticipate that the time to read all images may lead to fatigue. Therefore, the RP shall be permitted to read images for a period of no more than two hours, at which time the RP must take a minimum one-hour break before continuing with the rest of the assigned readings.

The SC shall confirm all entries are filled in. The SC, scanning technician or RP shall record if any protocol deviation or device deficiency is observed. The SC shall report to sponsor if any such events have occurred and ensure the event is resolved per study and institutional procedures.

Different RPs will be used for each of the three substudies.

For the first two substudies: On the first day, each of 3 participating RPs will be required to conduct the first reading (R1) of their TIFF images in a random order with respect to the scanner (1, 2 or 3) and scan event (1 or 2) established by the statistician. After a minimum two-week washout period, the same RP will read the same set of slides again for the 2nd reading (R2) and another two-week washout period will occur before the 3rd reading (R3).

For the third substudy: Each participating RP, one at each of three sites, will be required to conduct the first and only reading (R1) of their TIFF images in a random order established by the statistician with the images produced only at their site.

7.8 Pilot Studies

Before the study starts, the sponsor may choose to conduct one or more optional pre-study mock pilot trials of certain key procedures, specifically the screening and enrollment, creation of FOVs, and reader pathologist detection of feature procedure. This pilot is an extension of the user acceptance testing and is to allow the sponsor to observe and optimize the combined operation and workflow of training, procedures and eCRF recordings to insure processes are operational as expected, and consistent amongst participants. In order to insure pilots are being done correctly, the sponsor and consultants may review pilot data and compare against de-identified pathology reports and scans of de-identified histochemical slides for that pilot case.

The pilot will include participation of the actual pathologists and scanning technicians who are assigned in the study. Each pilot may be a full or abbreviated test of the actual study procedure by those participants. Each pilot may use upwards of 10-20 de-identified cases from the archive. And, so to not interfere with the cases selection process, these pilot cases are to be selected with accession dates less than 1 year from non-active cases.

8. STATISTICAL CONSIDERATIONS

To minimize bias due to recall of FOVs from previous reads, different reader pathologists will be used in the 3 different substudies.

8.1 Intra-Scanner Precision Substudy

This substudy includes one site with three scanners (called scanner A, scanner B, and scanner C). The random ordering of slides for the study and the sham slides is described below. The 378 study slides will be divided equally into three sets of 126 slides, 42 slides from each of 3 viewing magnifications (called set1, set2, and set3) using stratified randomization and the three sets randomly ordered into six possible combinations (123, 231, 312; 132, 213, 321). These six combinations create twelve 3x3 Latin Squares. One combination of the sets (1 of the 12 Latin Squares) will be randomly selected (say Latin Square 1 [123, 231, 312] as shown in the table below). Each number appears once on each row and on each column and each number represents a set of 126 slides, where each row and each column adds up to 378 slides.

Latin Square 1:			
	Column1	Column2	Column3
Row1	1	2	3
Row2	2	3	1
Row3	3	1	2

Each number appears once in each row and column. The number refers to a set.

Assigning 378 Slides to Each Reader:

Step 1 - For a selected Latin Square there are 6 possible choices for assigning the rows to the 3 readers. These choices are:

Pathologist	Choices for Assigning Each Combination to a Reader					
	1	2	3	4	5	6
Reader 1	123	123	231	312	312	231
Reader 2	231	312	123	123	231	312
Reader 3	312	231	312	231	123	123

One option will be randomly chosen and assigned to readers. Suppose the selected option is choice 3. Then combination 231 will be assigned to Reader 1, combination 123 will be assigned to Reader 2 and Reader 3 will be assigned combination 312.

Step 2 - Then the combination will be assigned to three scanners in such a way that the first number of the combination is assigned to Scanner A, the second number is assigned to scanner B and the third number is assigned to Scanner C. For Reader 1 the combination is 231 and the 126 slides in each set is assigned to each of three scanners as shown below:

Scanner	Set
Scanner A	2
Scanner B	3
Scanner C	1

Step 3 - On each scanner the 126 slides will be scanned three times (called iteration1, iteration2, iteration3) with at least six hours downtime (ensuring full cool down) of the scanner between scanning iterations as shown below:

Scanner	Iteration		
	Iteration 1	Iteration 2	Iteration 3
Scanner A	2.1 [Set 2, Iteration 1]	2.2	2.3
Scanner B	3.1	3.2	3.3
Scanner C	1.1	1.2	1.3

Step 4 – From above scanner by iteration table one of six random 3x3 Latin Square can be created for the three scanners and three reading sessions for a given reader such that for a given session each set comes from a different scanner and a different iteration. One selected 3x3 Latin Square is given in [Table 3](#) for three reading sessions for reader 1.

Table 3: Procedure to Randomly Select 378 Slides from Combination of Scanners and Iterations for Reader 1

		Reading Session		
		1	2	3
Set	1	Scanner C, iteration 2 1.2 (n=126)	Scanner C, iteration 1 1.1 (n=126)	Scanner C, iteration 3 1.3 (n=126)
	2	Scanner A, iteration 1 2.1 (n=126)	Scanner A, iteration 3 2.3 (n=126)	Scanner A, iteration 2 2.2 (n=126)
	3	Scanner B, iteration 3 3.3 (n=126)	Scanner B, iteration 2 3.2 (n=126)	Scanner B, iteration 1 3.1 (n=126)
Total		378	378	378
Set1, set2, and set3 do not need to be equal, but they need to add up to 378 slides and each set should have equal number of slides from each of 3 viewing magnifications				

Three separate reading sessions will be performed by each of three reading pathologists, with a washout period of at least two weeks between reading sessions. All 162 sham slides will be scanned once on scanner A. Per reading session, stratified randomization will be used to select 54 different sham slides (18 for each sham feature of a specific viewing magnifications) to add to each reading session such that all 162 sham slides will be read by each reading pathologist. The rotation of the FOV will be randomly determined in 90-degree intervals (0° [no rotation], 90°, 180°, 270°).

Then the reading sessions for reader 1 can be displayed as follows using [Table 3](#):

Session 1 reading for Reader 1 is combination of (1.2, 3.3, 2.1 + 54 sham slides)

Session 2 reading for Reader 1 is combination of (1.1, 2.3, 3.2 + 54 sham slides)

Session 3 reading for Reader 1 is combination of (2.2, 1.3, 3.1 + 54 sham slides)

As can be seen, each element of a given reading session comes from different rows and columns of the scanner by iteration table.

The process described above for Reader 1 will be repeated for readers 2 and 3. At the end, all 378 slides are scanned by each scanner and read by each reader.

8.1.1 Required Number of Slides

The precision will be based on three reading pathologists' assessments and identification of specific histologic features that are observed in TIFF images of FOV of FFPE H&E slides containing a primary feature. The twenty one (21) study features and 9 sham features selected for this study are provided in [Table 1](#). Each selected feature will be selected from at least three organs. There will be 6 FOVs per organ within each combination of feature-magnification. The 21 study features will be evaluated at their relevant magnification. The levels of viewing magnification will be 10x, 20x, and 40x. Each level of magnification will include seven study features.

For each study feature, three organs will be selected. For each organ, six FOVs will be selected, and it is assumed that each FOV contains one primary feature. Thus, the required number of study slides is

21 study features x 3 organs/study feature x 6 FOV/organ = 378 slides, which include selected study features and selected FOVs (see [Table 4](#)).

Table 4: Required Number of Slides with Selected Features and Selected FOVs		
Feature	Organ	Slides with Selected Feature & FOVs
1	1	1-6
1	2	7-12
1	3	13-18
2	1	19-24
2	2	25-30
2	3	31-36
.	.	.
.	.	.
.	.	.
.	.	.
21	1	361-366
21	2	367-372
21	3	373-378

In addition to the 378 FOVs selected for this study, 9 sham features, 3 for each viewing magnifications will be used. The number of sham slides is (3 viewing magnifications) x (3 features per magnification) x (3 organs per feature) x (6 FOVs per organ) = 3 x 9 x 6 = 3 x 54 = 162 sham slides, which include selected features and selected FOVs. The 162 sham FOVs will be selected from other glass slides. Sham FOVs will be used to minimize or avoid bias by the RP, but will not be included in any analysis. Thus, the total FOV set for the feature study is 540 FOVs.

8.1.2 Statistical Analysis of Intra-Scanner Precision

Each of three scanners will scan one-third of the slides three times; three RPs evaluate all scanned slides across three reading sessions. [Table 5](#) shows number of comparison pairs for each scanner.

Table 5: Intra-Scanner Pairwise Comparison	
Scanner	Number of Comparison Pairs
Scanner A	1134
Scanner B	1134
Scanner C	1134
Overall	3404

The number of comparison pairs, that is 1134, is calculated based on three RPs where for each RP there are three pairwise comparisons, namely scan1 vs. scan2, scan1 vs. scan3, and scan2 vs. scan3, which results in 3 reader x 126 pairs per comparison x 3 pairwise comparisons =1134 (see [Table 6](#)) comparisons per scanner.

Table 6: Number of Comparison Pair Per-Scanner

Scanner 1	Reader	Number of Pairwise Comparisons			Total # of Pairwise Comparisons
		Scan1 vs. Scan2	Scan1 vs. Scan3	Scan2 vs. Scan3	
	1	126	126	126	378
	2	126	126	126	378
	3	126	126	126	378
					1134

To evaluate Intra-Scanner precision for scanner A, three (3) single 2x2 tables can be constructed for pairwise comparison within scanner A and Reader1. [Table 7](#) demonstrates a 2x2 table for the pairwise comparison of scan1 versus scan2 for Reader1.

The result of reading for each slide is “Yes” or “No” if the primary feature was detected correctly. Each primary feature shall be considered as of equal importance as the next primary feature; thus, the results of all primary features will be pooled.

Table 7: Intra Scanner/Inter Scan Precision for Scanner A

		Feature is correctly identified using scan2		
		Yes	No	
Feature is correctly identified using scan1	Yes	a	b	a+b
	No	c	d	c+d
		a+c	b+d	126

Nine (9) 2x2 Tables will be pooled within scanner A and across 3 readers to create [Table 8](#) for $scan_{ki}$ versus $scan_{kj}$ for Readers k (k=1,2,3) and $i \neq j$ (for $i=1, 2, 3$ and $j > i$).

Table 8: Intra Scanner/Inter Scan Precision for Scanner A and all 3 Readers

		Feature is correctly identified using $scan_j$		
		Yes	No	
Feature is correctly identified using $scan_i$	Yes	a^1	b^1	a^1+b^1
	No	c^1	d^1	c^1+d^1
		a^1+c^1	b^1+d^1	1134

Then the Agreement Rate for each Scanner=(a^1+d^1)/1134 and 95% confidence interval (CI) will be estimated as shown in [Table 9](#).

Table 9: Intra-Scanner Results				
	Number of Pairwise Agreement	Number of Comparison Pairs	Agreement Rate	
			%	95% CI
Scanner A	a^1+d^1	1134	(a^1+d^1)/1134	
Scanner B	a^2+d^2	1134	(a^2+d^2)/1134	
Scanner C	a^3+d^3	1134	(a^3+d^3)/1134	
Overall	a^*+d^*	3402	(a^*+d^*)/3402	

The overall Intra-Scanner agreement rate will be calculated by averaging all pairwise comparisons results over all 378 slides with selected study features enrolled and all three pathologists. The overall number is 378 slides with selected features x 3 scanners x 3 readers = 3402. To preserve the correlation structure of multiple readings of the same feature and possibly multiple features on an FOV, the bootstrap method will be used to derive a two-sided 95% CI for the overall agreement rate. An FOV will be the bootstrap re-sampling unit.

Above analyses will be performed for primary feature.

The study acceptance criterion is 85%. The lower limit of the 95% CI for the overall agreement rate will be compared to 85% and if the lower limit is greater than 85%, then the study will have demonstrated intra-scanner precision.

In addition to the overall agreement given in [Table 9](#), overall average positive agreement (APA) and overall average negative agreement (ANA) will be provided with their corresponding two-sided 95% CIs.

In [Table 8](#), the percent agreement of scan i with scan j for a positive result is called positive percent agreement (PPA) and is defined as

$$PPA = a^1/(a^1+c^1)$$

The percent agreement of scan i with scan j for a negative result is called negative percent agreement (NPA) and is defined as

$$NPA = d^1/(b^1+d^1)$$

When obtaining PPA or NPA, one cannot assume either scan i or scan j is the reference. Thus, it is suggested that a reasonable summary of positive agreement between two scans is an average of the two PPAs, and a reasonable summary of negative agreement is an average of the two NPAs. These averages should be weighted to reflect the different marginal totals that are used when scan i or scan j is used as the reference. Clinical and Laboratory Standards Institute (28) defines APA and ANA as follows:

$$APA = 2 a^1/(2a^1+b^1+c^1)$$

$$ANA = 2 d^1/(c^1+b^1+2d^1)$$

Table 10 provides the overall APA and overall ANA rates with corresponding 2-sided, 95% CIs by pooling all pairwise comparisons over the three scanners.

Table 10: Intra-Scanner Overall APA and Overall ANA Rates					
	Number of Pairwise Agreement	APA Agreement Rate		ANA Agreement Rate	
		%	95% CI	%	95% CI
Overall	a^*+d^*	$2a^*/(2a^*+b^*+c^*)$		$2d^*/(c^*+b^*+2d^*)$	

8.1.3 Statistical Analysis of Secondary Features

The presence of secondary features in the FOVs is expected to be sparse because the FOV is selected for a specific primary feature.

The objective of the analysis is to investigate the frequency distribution of the absence or presence of the secondary features. Each feature will be considered primary for 18 FOVs (3 organs x 6 FOVs per organ) and will be considered secondary for the remaining 360 FOVs (this means n_1 of the 18 FOVs in set 1, n_2 of 18 FOVs in set 2, and n_3 of 18 FOVs in set 3, where $n_1+n_2+n_3=18$). It is possible that a given feature may not be present in the majority of the 360 FOVs.

The secondary analysis will be based on the repeatability/reproducibility regarding each secondary feature separately. To perform the secondary analysis for a specific feature, say feature X, 3 scans (scan1, scan2, and scan3) per scanner will be used. In the 3 scans from scanner A, there are n_1 FOVs primary for feature X among 126 FOVs and $126-n_1$ FOVs secondary for feature X. Thus, $126-n_1$ FOVs will be used to construct the following 2x2 contingency table.

Table 11: Intra Scanner/Inter Scan Secondary Analysis for Scanner A					
		Secondary Feature X is Observed Using Scan2			
		Yes	No		
Secondary Feature X is Observed Using Scan1	Yes	a	b	a+b	
	No	c	d	c+d	
		a+c	b+d	$126-n_1$	

Nine (9) 2x2 tables will be pooled within scanner A and across 3 readers to create [Table 12](#) for scan_i versus scan_j for reader k ($k=1,2,3$) and $i \neq j$ (for $i=1,2,3$ and $j>i$).

Table 12: Intra-Scanner/Inter-Scan Secondary Analysis for Scanner A Across all 3 Readers

		Secondary Feature is Observed Using Scan _i		
		Yes	No	
Secondary Feature is Observed Using Scan _i	Yes	a ¹	b ¹	a ¹ +b ¹
	No	c ¹	d ¹	c ¹ +d ¹
		a ¹ +c ¹	b ¹ +d ¹	1134 – 3(n ₁ +n ₂ +n ₃)

Repeatability and reproducibility of the reading results (i.e., overall APA and overall ANA) will be provided as shown in [Table 13](#) for each of the 21 features that appear as secondary features. In total, up to 21 contingency tables, one for each secondary feature, will be provided, based on the 3240 (3402 – 9 x 18) pairwise comparisons across all 3 readers and all 3 scanners.

Table 13: Overall APA and Overall ANA Rates for Secondary Feature Analysis

	Number of Pairwise Agreement	APA Agreement Rate	ANA Agreement Rate
		%	%
Overall	a [*] +d [*]	2a [*] /(2a [*] +b [*] + c [*])	2d [*] /(c [*] + b [*] +2d [*])

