METHODOLOGY Pathologists will be asked to identify a particular histological feature present in a field of view (FOV) image from the WSI image of a single slide. The slides will be selected and will contain one particular screened and enrolled feature from an organ at a particular magnification as listed in Table 1 . From these images, a TIFF image demarking the feature(s) of interest in a particular FOV will be created representing only a small discrete region of the entire slide consistent with field viewed at 10, 20 or 40x. The TIFF images will then be presented to the pathologist who will be asked to identify the feature(s) in the FOV from a list of possible multiple-choice features. Additionally, “sham” images of known features will be inserted into the reading deck to reduce recall bias, but will not be included in the analysis. Then, depending on the sub-study, the slide will be scanned three times on 1 scanner, or once on 3 different scanners. For the intra-scanner substudy, three scanners will be used, the slides will be divided equally among the scanners and scanned 3 times per assigned scanner for a given reading pathologist, and each of 3 pathologists will identify the features across 3 reading sessions separated by a 2-week wash out period between readings. For the inter-scanner substudy, 3 scanners will be used, the slides will be scanned once per scanner and 3 separate

pathologists will identify the features.

For the inter-site substudy, 3 sites, each with one scanner, will be used. The set of enrolled slides will be sent to site 2 and 3. These slides will be scanned once per scanner and 1 separate pathologist per site will identify the features in this substudy.

NUMBER OF SLIDES

A total of 21 features, 7 features at each of 3 viewing magnifications (10x, 20x, 40x), 3 organs within each feature, and 6 slides within each feature-organ combination resulting in 378 FOVs. There will be a total of 9 sham features, 3 at each of 3 viewing magnifications (10x, 20x, 40x), and 18 slides for each sham feature, within each sham features-magnification combination resulting in 162 FOVs sham slides.. The slides will be selected in consecutive order starting with slides at least 1 year old. An enrolling pathologist will screen and enroll the slides per the inclusion and exclusion criteria, which will be verified by a separate validation enrolling pathologist.

MAIN CRITERIA FOR INCLUSION / EXCLUSION

- Inclusion criteria:

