#### **6.4.3 Secondary Features**

The objective of this analysis is to investigate the repeatability/reproducibility of the readers' absence or presence calls of the secondary features. For a given magnification, each of the 7 features will be considered primary for 18 study FOVs (3 organs x 6 FOVs per organ) and will be considered secondary for the remaining 108 (6 primary features with the same magnification x 3 organs x 6 FOVs per organ) study FOVs.

It is possible that a given feature may be absent from the majority of the 108 study FOVs. Sham features are not considered.

The secondary features analysis will be based on the repeatability/reproducibility for each secondary feature separately. To perform the secondary analysis for a specific feature, say feature X, 3 scans (Iteration 1, Iteration 2, and Iteration 3) per scanner will be used. In the 3 scans from Set 1 on Scanner A, there are 6 FOVs primary for feature X among 42 FOVs and 36 FOVs secondary for feature X. Thus, 36 FOVs will be used to construct a 2x2 table for whether the secondary feature was observed.

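### Protocol 8.1.3 counts each feature as secondary in 360 FOVs (3240 pairs), but the reading form offers it on only 108 of them (972 pairs, as in the SAP), which inflates ANA in a descriptive analysis

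*Protocol*

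**What the plan says.** The design is set out in the Protocol synopsis: "A total of 21 features, 7 features at each of 3 viewing magnifications (10x, 20x, 40x), 3 organs within each feature". Protocol 8.1.1 gives the slide count as "21 study features x 3 organs/study feature x 6 FOV/organ = 378 slides", one primary feature per FOV.

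For secondary features, Protocol 8.1.3 states: "Each feature will be considered primary for 18 FOVs (3 organs x 6 FOVs per organ"), and that the same feature "will be considered secondary for the remaining 360 FOVs". Table 11 takes all of a set's FOVs except those primary for the feature (126 minus n1). The contingency table for each feature is then "based on the 3240 (3402 – 9 x 18) pairwise comparisons across all 3 readers and all 3 scanners". Table 13 reports APA and ANA as rates, and the number of agreeing pairs, a* + d*, as a count. Protocol 8.2 and 8.3 refer back to 8.1.3 for the other two substudies.

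Protocol 7.7 describes the reading task: the reader identifies features "against a list of 10 possible choices, i.e., the 7 study feature and 3 sham features for that magnification". Section 4 says the same. The inclusion criteria (5.2.1) and the enrolling pathologist's recording (7.3) also confine secondary features to the FOV's own magnification group.

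SAP 6.4.3 uses a different population. Within a magnification, each feature "will be considered secondary for the remaining 108 (6 primary features with the same magnification", times 3 organs and 6 FOVs per organ. This leads to 324 pairs per scanner and 972 overall. SAP 6.6.3 gives 324 pairs for the inter-site substudy.

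**The concern.** Protocol Table 1 lists 30 features, 10 per magnification, and none appears under two magnifications. A 10x feature is therefore never offered on the form for a 20x or 40x FOV. Those FOVs produce no reading for it, yet protocol 8.1.3 includes them in its tables. The section thus contradicts the protocol's own form and its own definition of a secondary feature, as well as the SAP.

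What is at stake is the meaning of ANA for secondary features. Pairs with no reading behind them can enter only as agreement on absence, so the distortion always favours the device. The SAP says it should be read together with the protocol, but neither document says which prevails where they differ.

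**Working it through.** **Inputs.** 21 features, 7 per magnification, 3 organs, 6 FOVs per organ (Protocol 1.1 and 8.1.1); 10 same-magnification choices on the form (Protocol 4 and 7.7); 3 readers, each giving 3 pairwise comparisons per FOV (Protocol 8.1.2).

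**Step 1: reproduce the protocol's figure.**
- FOVs: 21 × 3 × 6 = 378. Primary for one feature: 3 × 6 = 18. Remainder: 378 − 18 = 360.
- Pairs per FOV: 3 readers × 3 comparisons = 9. So 360 × 9 = 3240, which equals 3402 − 9 × 18.
- Per scanner: 1134 − 3 × 18 = 1080, and 1080 × 3 = 3240.

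The protocol's arithmetic is exact. The fault lies in which FOVs are counted.

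**Step 2: count only FOVs whose form lists the feature.**
- Per magnification: 378 / 3 = 126 FOVs. Less the 18 primary ones: 108.
- Pairs: 108 × 9 = 972, or 108 × 3 = 324 per scanner. Both match SAP 6.4.3.
- Not offered: 360 − 108 = 252 FOVs, or 252 × 9 = 2268 pairs; 2268 / 3240 = 70%.
- Inter-site, with 3 pairs per FOV: 360 × 3 = 1080 on the protocol's approach, against 108 × 3 = 324 in SAP 6.6.3.

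**Step 3: effect on the reported rates.** The protocol defines APA = 2a/(2a + b + c) and ANA = 2d/(2d + b + c). If unlisted features are coded No, the 2268 pairs all fall in cell d. APA does not use d and does not move. The count a* + d* rises by 2268. For ANA, with cell values assumed for illustration:

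| Assumed cells among the 972 pairs | d on 972 | ANA on 972 | d on 3240 | ANA on 3240 |
|---|---|---|---|---|
| a = 20, b + c = 40 | 912 | 1824/1864 = 97.9% | 3180 | 6360/6400 = 99.4% |
| a = 50, b + c = 100 | 822 | 1644/1744 = 94.3% | 3090 | 6180/6280 = 98.4% |

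**Step 4: how far it can go.** Setting b + c = 972, so that no scorable pair agrees, gives ANA = 4536/(4536 + 972) = 82.4%. This is an arithmetic bound that real data cannot reach: three Yes/No readings of one FOV always contain at least one agreeing pair, so at most two-thirds of pairs, 648, can disagree. If every trio is two Yes and one No, then a = 324, b + c = 648 and d = 0. ANA is then 0% on 972 pairs but 4536/(4536 + 648) = 87.5% on 3240.

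**Step 5: the statistics also differ.** With a = 50, b + c = 100 and 972 pairs, the protocol's APA is 100/200 = 50%, while the SAP's positive agreement is 50/972 = 5.1%. The protocol's ANA is 94.3%, while the SAP's negative agreement is 822/972 = 84.6%. Aligning the counts alone would leave this conflict in place.

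**The case against.** The strongest reply is that the SAP is the analysis document and already specifies this analysis on the right FOVs for all three substudies. The inflated ANA would appear only if someone worked from protocol 8.1.3, and the SAP does not compute ANA at all. This carries weight and lowers the severity. It does not remove the point: the protocol text is current, no precedence rule is stated, and the SAP does not present its count as a correction.

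A second reply is that the protocol never says unlisted features are scored No. That is so, and the coding is an inference. But if those FOVs are instead treated as missing, the stated 3240 cannot be reached and the tables cannot be built as described. The section fails on either reading.

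A third reply is that the analysis is descriptive. Its aim is to describe how often secondary features are present or absent, it has no acceptance criterion, and Table 13 carries no confidence interval. This stands.

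Three stronger inferences are tempting and are not supported:
- A reader might infer that ANA approaches 100% whatever the readers do. Step 4 shows otherwise.
- A reader might infer that the protocol would report an inflated overall agreement rate for secondary features. It defines no such rate there, only the count a* + d*. The overall rate is the SAP's, over 972.
- A reader might infer that the pass/fail result is affected. The 85% criterion rests on primary features only.

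**Conclusion.** Protocol 8.1.3 is wrong as written. It claims 360 FOVs and 3240 pairs per feature where its own form can supply 108 and 972, so 70% of the pairs have no reading behind them. If the stated total is honoured through No coding, ANA is biased upward (about 4 percentage points in the second example, 1.5 in the first) and the agreement count is overstated by 2268.

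The protocol-SAP conflict in the counts follows from the documents alone. The size of the ANA effect rests on the inferred coding and on assumed cell values, since the documents give no expected rates for secondary features.

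This is an error in defining the analysis population, not an arithmetic slip. Severity is low: APA and the primary-feature conclusion do not change.

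**What to change.** Amend protocol 8.1.3 and Tables 11 to 13 so that a feature is secondary only in FOVs of its own magnification group, and let 8.2 and 8.3 follow by reference. The counts become:

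- 108 FOVs per feature.
- Intra-scanner: 324 pairs per scanner and 972 overall.
- Inter-scanner: 972 pairs overall.
- Inter-site: 324 pairs.

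The total in Table 11 becomes 42 − n1. This equals 36 under the SAP's stratification by feature and organ (SAP 4.1.1), which puts 6 primary FOVs per feature in each set. Protocol 8.1 promises balance by magnification only, and 8.1.3 allows unequal n1, n2 and n3. If the protocol is to state 36 per set, it should adopt the SAP's stratification. The totals of 324 and 972 hold either way.

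In the same amendment, reconcile the secondary-feature statistics: either the protocol's APA and ANA or the SAP's a*/972 and d*/972, defined identically in both documents.

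The cost is wording in the protocol, and in the SAP if its statistics change. No new slides, scans or readings are needed. Any ANA reported would be lower than under the present protocol count.
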